8. IMMUNOGENICITY ANALYSES

The Immunogenicity analyses will be based on the "Safety" population, unless otherwise specified. The immunogenicity analysis summarises the incidence of anti-drug antibodies and lists the titre of immunogenicity results.

Details of the planned displays are presented in Appendix 12.

201247

9. PHARMACOKINETIC ANALYSES

Pharmacokinetic data will be presented in graphical and/or tabular form and will be summarized descriptively. All pharmacokinetic data will be stored in the Archives, GlaxoSmithKline Pharmaceuticals, R&D.

Correlation analysis will be performed and presented as scatter plots including Pearson correlation coefficient for Measured Steady State Concentration vs Baseline Body Weight, Haemoglobin and Platelet Nadirs as Percentage Change from Baseline vs Measured Highest Concentration by treatment groups.

9.1. Primary Pharmacokinetic Analyses

See Section 10 for PopPK analysis and Section 12 for PK/PD analysis.

201247

10. POPULATION PHARMACOKINETIC (POPPK) ANALYSES

GSK2330811 plasma and Total OSM serum concentration-time data will be analysed by population pharmacokinetic/pharmacodynamic (PopPK/PD) methods using a non-linear mixed-effects modelling approach.

The objective of the PopPK analysis is to develop a population PK model that characterizes the PK of GSK2330811 following repeat subcutaneous administration in patients with dcSSc. The individual participant PK parameters will be estimated and documented for the purposes of any subsequent exposure-response (PK/PD) analyses.

10.1. Statistical Analyses / Methods

See Appendix 10 for details.

To support this analysis a PK/PD dataset will be generated. The details for the dataset specifications are provided in Appendix 9

10.1.1. Endpoint / Variables

10.1.1.1. Drug Concentration Measures

Refer to Appendix 5(Section 16.5.3 Reporting Standards for Pharmacokinetic)

10.1.1.2. Derived Pharmacokinetic Parameters

In addition to the parameters of the PopPK model itself, individual participant parameters will be estimated from the PopPK model i.e. empirical Bayes estimates will be reported (also known as post-hoc parameter estimates).

Parameter	Parameter Description
Apparent Clearance	Individual participant estimate of apparent clearance (empirical Bayes estimates)
Apparent Volume of Distribution	Individual participant estimate of apparent volume of distribution (empirical Bayes estimates)
AUC	Individual model predicted AUC at steady state

• NOTES: Additional parameters may be included as required.

10.1.2. Summary Measure

The population PK parameter will be used to describe the population so therefore parameters will not be summarised across participants.

10.1.3. Population of Interest

The standalone PopPK analysis will be based on the "Pharmacokinetic" (PK) population, unless otherwise specified. If the simultaneous PopPK/PD model can be developed, then the analysis will be based on the PK population.

201247

10.1.4. Strategy for Intercurrent (Post-Randomization) Events

PK and PK/PD models will use all available data and will not account for intercurrent events (i.e. will adopt a 'while on treatment' strategy).

10.1.5. Statistical Analyses / Methods

Details of the planned displays are provided in Appendix 12 and will be based on GSK Data Standards and statistical principles.

201247

11. PHARMACODYNAMIC ANALYSES

The endpoints OSM Free and OSM Total make up the primary pharmacodynamic endpoints in this study. Data will be presented in graphical and/or tabular form and will be summarized descriptively. Individual results will be reported in listings and Figures; summary results will be reported in tables and Figures.

201247

12. PHARMACOKINETIC / PHARMACODYNAMIC ANALYSES

OSM Free and OSM Total will be analysed through the PK/PD models specified in Appendix 10.

The objective of this analysis is to develop a population PK/PD model that characterizes the PK of GSK2330811 and the total OSM concentration-time profile following repeated subcutaneous administration of GSK2330811 in patients with dcSSc.

Exposure/ response analysis for haematology (platelets and haemoglobin) will be a pooled analysis that includes all available clinical data generated with GSK2330811. This pooled analysis will be described in a separate document.

Exposure/ response and or joint analysis for clinical endpoints and biomarkers will be done ad-hoc post SAC, based on the results of the statistical analysis.

12.1. Statistical Analyses / Methods

The analysis aims to characterise the relationship between plasma concentrations of GSK2330811, and target OSM concentration (total). Predicted TE% will be derived as defined in Section 16.6.5. Predicted values for free OSM will be used if measured values are below the LLQ of the assay.

Detailed PK/PD methodology is presented in Appendix 10

To support this analysis a PK/PD dataset will be generated. The details for the dataset specifications are provided in Appendix 9

Any exposure/ response and or joint analysis for clinical endpoints and biomarkers will be initiated post SAC, based on the results of the statistical analysis. The dataset to support this analysis and the analysis plan will be described in a separate document.

201247

13. BIOMARKER ANALYSES

Exploratory biomarker analysis will take place at the final SAC.

13.1. Primary Biomarker Analyses

13.1.1. Endpoint / Variables

The following endpoints will be collected and presented in the outputs. Only systemic endpoints will be presented at baseline for IA2.

13.1.1.1. Systemic:

13.1.1.1.1. Fibrosis markers:

- Pro-C3
- C3M
- Pro-C6
- C6M
- PINP
- C1M (Note: Cohort 1 assay used antibody generated using mouse hybridoma cell line (old C1M kit). Cohort 2 assay used recombinant detection antibody, these will be summarised and plotted separately)
- COMP
- PIIINP
- HA
- TIMP-1

13.1.1.1.2. Derived fibrosis markers:

- Pro-C3/C3M (ratio)
- Pro-C6/C6M (ratio)
- PINP/C1M (ratio) (Note for C1M, Cohort 1 assay used antibody generated using mouse hybridoma cell line (old C1M kit). Cohort 2 assay used recombinant detection antibody, these will be summarised and plotted separately)
- Enhanced Liver Fibrosis (ELF) test (a linear combination of hyaluronic acid (HA), amino-terminal propeptide of type III Procollagen (PIIINP, a measurement of collagen III synthesis) and tissue inhibitor of metalloproteinase 1 (TIMP-1) in serum, this derived score will be provided by the vendor

13.1.1.1.3. Inflammation markers:

- CRP
- IL-6
- MCP-1 (Rename MCP-1 as CCL2 for displays)
- CCL-18

201247

13.1.1.1.4. Vascular markers:

- vWF
- VEGF
- sVCAM-1
- NT-ProBNP

13.1.1.2. Skin Histology

• Alpha Smooth Muscle Actin (αSMA)

(Note: During the review process of Alpha SMA samples, some samples were found to have insufficient tissue due to shallow biopsies. Summaries, stats analysis and plots exclude those insufficient samples. Additional summary and plots will be produced on the full data (including both the sufficient and insufficient samples.)

13.1.1.3. Skin Gene expression RNA Sequencing:

13.1.1.3.1. Individual Genes of Interest:

- Inflammation genes: CCL2, CCL18, MS4A4A
- Fibrosis genes: THBS1, COMP
- PD marker at the site of action: SOCS3
- Target expression in skin: OSM, OSMR

13.1.1.3.2. Derived Gene:

• 2-gene SSc skin biomarker: 2GSSc (See Section 16.6.6 for derivation)

13.1.1.3.3. Gene Set Variation Analysis (GSVA) Score

GSVA (Hanzelmann, 2013) assesses the relative enrichment of a gene set of interest across all samples and generates an enrichment score for each gene set per individual sample. The algorithm will first calculate expression-level statistic for each gene using all the provided samples' gene expression distribution and subsequently rank the genes. Based on the expression-level statistic, the algorithm will then assess if the genes in the gene sets of interest are more likely to be enriched at either end of the ranking. The input of GSVA will be the rlog normalized and transformed expression matrix and the output of GSVA will be enrichment scores bound between 1 and -1 for each individual sample.

13.1.1.3.4. Disease signature

A broad set of public microarray datasets were used to create a systemic sclerosis gene signature in skin consisting of 251 individual genes, some of which are up-regulated and some of which are down-regulated in SSc skin compared to healthy skin (see Appendix 13 and eLNB reference number N76598-1 Section 2.1 and Section 3.1). The systemic sclerosis gene signature will be quantified using GSVA score.

- Individual Gene Sets: 209 Upregulated Genes and 42 Downregulated Genes
- Disease Signature: GSVA Scores (Upregulated and Downregulated)

201247

13.1.1.3.5. Lung Fibrosis Signature

A broad set of public microarray datasets were used to create a lung fibrosis signature consisting of 42 individual genes. These genes can be detected in the skin and therefore lung fibrosis gene dysregulation can be evaluated in the skin biopsies. The lung fibrosis signature will be quantified using GSVA score. (see Appendix 13 and eLNB reference number N76598-1 Section 2.4 and Section 3.4).

13.1.1.3.6. Cell Module Signatures

The aim of the cell modules is to assess the effect of GSK2330811 on different cell-types and to compare the effect of GSK2330811 with the published tocilizumab data. The cell modules consist of three gene sets derived from Khanna, 2016b: Fibrosis (Table S3), M1-Macrophage (Table S7) and M2-Macrophage (Table S8). Cell module signatures will be quantified using GSVA score. (see Appendix 13)

- Individual Gene Sets: 37 Fibrosis Genes, 32 M1-Macrophage Genes and 31 M2-Macrophage Genes.
- Cell Module Signatures: GSVA Scores (Fibrosis, M1-Macrophage and M2-Macrophage)

13.1.2. Summary Measure

Interim 2:

The baseline values will be summarised without treatment groups using the safety population presenting summary statistics assuming a skewed distribution for the systemic markers. A scatter plot of the raw baseline values will be presented alongside the geometric mean \pm standard error.

The Spearman's and Pearson's correlations of the baseline values transformed using log base 10, will be calculated and presented for each combination of endpoints. The correlations will also be presented as scatter plots for each pair of endpoints. Where both the correlations are >-0.3 and <0.3 the correlation will be suppressed from the outputs.

Final analysis

Standard summaries at each planned timepoint will be used for biomarker endpoints assuming a skewed distribution. The ratio of the post-baseline to baseline values and fold change (geometric ratio <1 then fold change is -1/geometric ratio otherwise fold change is geometric ratio) will also be summarised.

Systemic biomarkers will be summarised and presented using a log 10 scale while the histology and gene sets will be summarised and presented using a log 2 scale. 2GSSc skin biomarker and GSVA Scores will be summarised and presented on linear scale.

Line plots of the unadjusted geometric means \pm standard error for log transformed data and unadjusted means \pm standard error for linear data will be presented by treatment group at each visit. Individual participant plots of the raw values will be presented by treatment group and individual plot lines are differentiated by MMF use at Day 1 (solid

201247

line denote subjects on mycophenolate at day 1 and dashed line denote subjects not in mycophenolate at day 1). Information on positive autoantibodies is added to the subject ids in the legend as per Section 6.1.

13.1.3. Population of Interest

For Interim 2 the summaries will be based on the "Safety" population.

For other reporting efforts, the primary biomarker analyses will be based on the "Per Protocol" analysis population, unless otherwise specified.

13.1.4. Strategy for Intercurrent (Post-Randomization) Events

Biomarker analysis will not account for intercurrent events (i.e. will adopt a 'while on treatment' strategy).

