8.1.1. Individual Safety Stopping Rules

Study treatment will be permanently discontinued in the event of any of the following:

- If a participant experiences a serious or clinically significant severe AE that in the opinion of the investigator, after consultation with the medical monitor, has a reasonable possibility of relation to GSK2330811 ([Appendix 4](#)).
- The participant becomes pregnant.
- The participant initiates a prohibited medication (Section [7.7.2](#)).
- The participant develops a serious infection.
- The participant experiences a severe or serious hypersensitivity reaction, including anaphylaxis (defined according to [Sampson, 2006](#)).
- The liver chemistry stopping criteria (Section [8.1.2](#)), QTc stopping criteria (Section [8.1.3](#)) or haematological stopping criteria (Section [8.1.4](#)) are met.

If the study treatment is discontinued, but the participant has received one or more doses of study treatment, the remaining study visits should still be performed including skin biopsy and home and laboratory FVC monitoring if this is deemed reasonable in the opinion of the Investigator and the participant is willing. In particular, the safety assessments should still continue as per protocol. The suction blister procedure will not be performed if study treatment is discontinued. If the participant declines any further follow-up and chooses to withdraw themselves from the study the investigator should make every effort to conduct the Early Withdrawal assessments as described in Section 8.2 and Section 2.

[figure not shown]

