13.1.5.1. Model Checking & Diagnostics

As an initial model fit 100,000 MCMC samples will be generated with a thin of 10, providing 10,000 samples to be used for the estimate of the posterior distribution. A burnin of 5,000 samples will be used. Starting values for the parameters will be based on the mode of the prior distributions.

The following list of convergence diagnostics will be applied for each parameter (diagnostic checking outputs will be stored in the refdata folder in HARP in the relevant reporting effort):

- The Monte Carlo Standard Errors (MCSE) should be compared with the standard deviation of the posterior distribution (SD) to ensure that only a fraction of the posterior variability is due to the simulation. The number of samples generated, and/or the thinning may be increased to reduce the ratio of the MCSE/SD as deemed necessary.
- Trace plots of samples versus the simulation index will be visually inspected to assess some aspects of convergence. The centre of the chain should appear stable with very small fluctuations, i.e., the distribution of points should not change as the chain progresses and the posterior mean and variance are relatively constant.
- Autocorrelation plots will be visually inspected to assess degree of autocorrelation (should decline rapidly and show no oscillation patterns).
- Density plots of the posterior for the model parameters will be plotted (should be smooth and with a single hump).

If the model is not deemed to have converged the following actions will be taken in the order described below:

- Increasing the number of MCMC samples and/or the thinning will be explored. The blocking of the parameters will be considered.
- For the joint model:
 - \circ The variance of the parameters used to model the baseline data may be considered as fixed, based on the observed variance of the parameter rather than using δ_i ~iGamma(shape=0.1, scale=0.1).
 - The endpoint with the most missing data will be removed from the model and the joint model carried out on the remaining 3 endpoints.
- For the MMRM model:
 - If missing data at the post-treatment visits are causing the nonconvergence, these visits will be removed and details included in a footnote.

201247 | Statistical Analysis Plan RAP Amendment 3 Final_V1 21 Aug 2020 | TMF-2068612 | 1.0

CONFIDENTIAL

201247

• Removal of covariates will be considered, starting with MMF use at day1, then the baseline by visit interaction (if applicable).

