14.1.4. Strategy for Intercurrent (Post-Randomization) Events

Exploratory efficacy analysis will not account for intercurrent events (i.e. will adopt a 'while on treatment' strategy).

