16. APPENDICES

16.1. Appendix 1: Protocol Deviation Management and Definitions for Per Protocol Population

16.1.1. Exclusions from Per Protocol Population

A participant meeting any of the following criteria will be excluded from the Per Protocol population:

Number	Exclusion Description		
01	Participant did not receive at least 4 doses of study treatment		
02	Placebo participant received active treatment		
03	Participant did not participate in at least one post-dose assessment		
04 ^[1]	Participant excluded on basis of final review of inclusion/exclusion criteria		
05 ^[1]	Participant excluded on basis of final review of the prohibited medication use		
^[1] Note: Da	^[1] Note: Data reviewed and decisions regarding exclusions from the Per Protocol population will be		

201247

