16.4. Appendix 4: Study Phases and Treatment Emergent Adverse Events

16.4.1. Study Phases

In general, assessments and events will be classified according to the time of occurrence relative to study treatment start date. Specific rules for Concomitant Medications and Adverse Events are specified in the section below.

Treatment Phase	Definition
Pre-Treatment	Date < Study Treatment Start
On-Treatment	Study Treatment Start ≤ Date ≤ Study Treatment Stop Date +28 days
Follow up	Study Treatment Stop Date +28 days < Date

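### At the final analysis the serum OSM summaries and every biomarker and efficacy model use only the Per Protocol population, which drops anyone with fewer than 4 doses, and no Safety-population repeat is planned

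*SAP*

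**What the plan says.** **Intercurrent events.** SAP 13.1.4: "Biomarker analysis will not account for intercurrent events". SAP 14.1.4: "Exploratory efficacy analysis will not account for intercurrent events". Both add the label *while on treatment*.

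**Population.** SAP 13.1.3: "For other reporting efforts, the primary biomarker analyses will be based on the" Per Protocol set. SAP 14.1.1 and 14.1.3 make the same choice for efficacy. SAP section 4 also assigns PD to Per Protocol, apart from the first two interims.

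**Exclusions.** SAP 16.1.1, item 01: "Participant did not receive at least 4 doses of study treatment".

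**Follow-up after stopping.** Protocol 8.1.1 asks that "the remaining study visits should still be performed including skin biopsy and home and laboratory FVC monitoring", if the investigator finds this reasonable and the participant is willing.

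**Dosing rules.** Protocol 8.1.4 stops treatment for confirmed haemoglobin below 80 g/L or platelets below 50x10^9/L. Protocol 8.1.5 withholds a dose for platelets from 50 to below 75x10^9/L. Protocol 3.2 attributes the platelet and red-cell falls in the first human study to inhibition of OSM.

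**Protocol populations.** Protocol 10.2 defines Enrolled, Safety and Pharmacokinetic, plus an evaluable criterion of at least 4 doses and both biopsies. It defines no Per Protocol population, and SAP 2.1 Table 1 does not record that one was added.

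**The concern.** Receiving fewer than 4 doses is an outcome of treatment as well as a matter of compliance. Low platelets or haemoglobin can cause it, and the protocol links both to the pharmacology that the OSM and biomarker endpoints are meant to show. Conditioning on it means that the randomised arms may no longer be comparable in the analysed set.

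The risk is not remote. Protocol 5.5 predicts no grade 2 or worse platelet fall at 100 mg but makes no such statement for 300 mg, which is the modelled dose. SAP 3.2 records an extra data review after a thrombocytopaenia-related temporary stopping criterion was met in another study of this drug.

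At stake are the proof-of-mechanism and exploratory efficacy estimates, and the final description of serum OSM. The primary safety analyses use the Safety population and are untouched.

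**Working it through.** **1. Who is removed.** Doses fall on Days 1, 15, 29, 43, 57 and 71 (Protocol section 2). Exclusion 01 applies when at most 3 are received, so at least 6 - 3 = 3 are not given. The routes are a permanent stop before Day 43, or three or more doses withheld or missed. Someone stopping after dose 4 or 5 stays in, with later values.

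**2. What is lost.** Suppose dosing stops after Day 29 and all later visits are attended. Post-baseline data on the schedule that are collected but not used in the final Per Protocol displays:

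| Data | Days | Visits used |
|---|---|---|
| Blood biomarkers | 29, 57, 85, 197 | 0 of 4 |
| Serum OSM | 15, 29, 57, 85, 113, 155, 197 | 0 of 7 |
| Skin biopsy | 85 | 0 of 1 |
| mRSS | 57, 85, 197 | 0 of 3 |
| Laboratory FVC, HAQ-DI | 85, 197 | 0 of 2 |

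**3. Where else the values could appear (SAP Appendix 12).**
- Modelled biomarker Tables 8.4, 8.8, 8.11 and 8.17-8.19, and modelled efficacy Tables 9.3, 9.6, 9.11 and 9.20: Per Protocol only.
- Serum OSM Tables 6.1-6.4: Per Protocol at the final analysis. Tables 6.2 and 6.4 use Safety at the first two interims, and 6.1 and 6.2 use it at the ad hoc review.
- Individual OSM plots (Figures 6.1, 6.2): Per Protocol at the final analysis.
- Serum OSM Listing 44: due at dose escalation and the first two interims, not at the final analysis.
- Figure 6.5 (median total OSM) uses the PK population. SAP 10.1.3 also names that population for the PopPK/PD model, although Tables 7.1-7.2 are labelled Per Protocol at the final analysis. Both may include excluded active participants, but not placebo.

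In the visible display list, then, an excluded participant's serum OSM values reach no final OSM table, individual plot or listing.

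**4. Will the populations differ?** No rate is given. Assuming a probability p of fewer than 4 doses, the chance that at least one of 15 active participants is removed is 1 - (1 - p)^15. This gives 54%, 79% and 96% for p = 5%, 10% and 20%.

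**5. Precision.** Protocol 10.1 quotes a half-width of 0.565 for log(PIIINP), with SD 0.521 and 15 versus 5 participants. Reproduced: t(0.975, 18 df) x SD x sqrt(1/15 + 1/5) = 2.101 x 0.521 x 0.5164 = 0.565. The same formula with fewer active participants:

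| Active removed | 0 | 1 | 2 | 3 | 4 |
|---|---|---|---|---|---|
| Half-width | 0.565 | 0.573 | 0.581 | 0.591 | 0.603 |

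The largest increase is 0.603/0.565 = 1.07, or 7%. If 1 of 5 placebo participants is also lost, 1 to 4 active removals give 0.626 to 0.657.

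**6. Bias.** With k of 15 active participants removed, the simple mean over all 15 differs from the mean over those retained by (k/15) x D. D is the mean of the excluded minus the mean of the retained. The documents fix neither the size nor the sign of D. Excluded participants may be those with the strongest drug effect. But for a last dose on Day 29 the Day 85 sample comes 56 days later, which is 56/25 = 2.2 to 56/19 = 2.9 half-lives (Protocol 5.4), so their response may have waned.

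**The case against.** **One answer, not a conflict.** A reader might infer that the SAP gives contradictory rules for an early stopper: use everything, use values up to "Study Treatment Stop Date +28 days" (SAP 16.4.1), or use nothing. The documents do not support that. Population decides who enters, and the intercurrent-event rule decides which of their values count. The early stopper is simply out. For those who remain, SAP 10.1.4 attaches the same label to using all available data. SAP 13.1.5.1 drops post-treatment visits only as a convergence remedy: "If missing data at the post-treatment visits are causing the nonconvergence". No text truncates biomarker or efficacy values 28 days after the last dose. The label is loose, but the rule can be recovered, so rewording it is clarification only.

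**The threshold is principled.** Four doses matches the protocol's evaluable criterion, and SAP 3.2 justifies Per Protocol at later interims as a way to assess repeat dosing. The models are exploratory and no formal hypothesis is tested. This stands, and it is why Per Protocol should remain the main analysis. It does not explain the absence of a companion estimate.

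**Exclusion may be rare.** Entry requires platelets of at least 150x10^9/L, stopping requires a confirmed count, and withholding alone must cost three doses. This is fair. If nobody is excluded, the proposed repeat produces nothing.

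**Safeguards exist.** Deviations are reviewed before unblinding, and Table 1.9 summarises exclusions. A note to Table 1.25 contemplates a Safety-population biomarker analysis, but none is specified. SAP 16.7.1 promises listing of withdrawn participants' data, but no final serum OSM listing is visible. It would also be too strong to say that no model can include these participants, given the PopPK/PD model.

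**SAP Table 1.** The protocol defers exploratory analyses to the analysis plan, so an entry there is arguably unnecessary for those endpoints. That deferral does not cover serum OSM as a secondary endpoint.

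**Conclusion.** The point holds as a cheap improvement. A post-randomisation exclusion that the drug itself can trigger governs every final biomarker and efficacy model and the final serum OSM summaries, and nothing planned shows whether it matters. The loss of precision is small: at most 7% for up to 4 of 15 active participants, on the protocol's PIIINP assumptions and an assumed number of exclusions.

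Two further inferences should be resisted. A reader might conclude that Per Protocol understates the drug effect and attach a figure. That would need an exclusion rate, a correlation between platelet fall and biomarker response, and a residual SD, none of which the documents give, and waning exposure could push the other way. A reader might also conclude that item 05, "Participant excluded on basis of final review of the prohibited medication use", removes participants for corticosteroid use begun late in follow-up, since no time window is visible. Its footnote is cut off in the available text, so the absence of a window cannot be inferred.

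**What to change.** 1. Keep Per Protocol as the main analysis.
2. Add to SAP Appendix 12: if the Per Protocol and Safety populations differ, repeat OSM Tables 6.1-6.4 and modelled Tables 8.4, 8.8, 8.11, 8.17-8.19, 9.3, 9.6, 9.11 and 9.20 in the Safety population with all observed visits.
3. In SAP 13.1.4 and 14.1.4, replace the *while on treatment* label with: *all observed visits, including those after the last dose, are used*.
4. List the Per Protocol population, and its use for serum OSM, in SAP 2.1 Table 1.

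Cost: two reworded sentences, one line in Table 1 and up to 4 + 10 = 14 extra tables, run only if the populations differ. The SAP already uses that condition for its demography and exposure tables. No new data and no protocol amendment are needed.
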